8.1 Sample Size Considerations

The sample size is based on the all-cause mortality up to Day 60. For the placebo (SOC) group, the proportion of subjects dead at Day 60 is estimated to 10% (Marconi et al., 2021).

With 150 evaluable subjects per trial group, there will be an 80% power to detect a difference between C21 and placebo if the proportion of subjects dead at Day 60 in the C21 group is 2.5% (corresponding to a Hazard Ratio of 0.24). In this calculation a 5% withdrawal rate has been assumed. For the actual detection limit (corresponding to 50% power), if 15 subjects die in the placebo group, significance will be seen if at most 6 subjects die in the C21 group.

This assumes using a 2-sided test at a 5% significance level. Analysis will be by intention-to-treat; thus, all randomized subjects should be accounted for in the statistical evaluation.

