8.2 Randomization

Subjects will be randomly assigned in a 1:1 ratio to C21 or placebo treatment. Subject randomization will use a randomly permuted block design and stratified by severity of disease (5 or 6) measured by the 8-point ordinal scale score on trial Day 1 and region.

Registration and randomization will take place using a centralized Interactive Web Response System (IXRS) contracted through Almac. At registration, the IXRS will assign a unique subject identification number that will be used on all of that subject's eCRFs and serious adverse event (SAE) report forms.

This is a double-blinded trial, only a few number of the trial team members are not blinded for conduct of the trial or ensuring subject safety purposes. The unblinded team members will include CRO DMC team members (statistician, programmers and project manager), CRO clinical supply program manager, CRO clinical system designer, CRO clinical system developer and CRO safety personnel. Details are provided in the Data Blinding and Documentation Plan.

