12.5.2.2 Primary Analysis

All-cause mortality at Day 60 will be defined as time to day of death from any cause within Day 1 to Day 60 follow-up (refer to Section 10.11). All-cause mortality will be estimated using the Kaplan-Meier methodology where subjects in this analysis without the event will be censored at Day 60 follow-up. Withdrawn subjects without the event will be censored at day of discontinuation (this assumes the censoring is non-informative).

Treatment groups will be compared using a stratified log-rank test adjusting for treatment, actual baseline disease severity and region. The p-value from the stratified log-rank will be presented. The size of the treatment effect will be estimated as a hazard ratio, obtained using a Cox proportional hazards regression model, and the Cox regression model will include a factor for randomized treatment, baseline disease severity and region. The estimated Hazard Ratio comparing C21 to Placebo will be presented together with the corresponding 95% CI (based on Wald test). A Kaplan-Meier plot of time to all-cause mortality will also be produced.

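### The Wald interval for the mortality hazard ratio can include 1 when the log-rank test is significant, and does not exist if no C21 subject dies; only the reported interval is affected

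*SAP*

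**What the plan says.** SAP 12.5.2.2 specifies two calculations for the primary endpoint. The p-value comes from a log-rank test stratified by actual baseline severity and region (pooled, per SAP 12.0). The effect size comes from a Cox model in which severity and region are factors, and the resulting hazard ratio "will be presented together with the corresponding 95% CI (based on Wald test". SAP 12.5.2.4 repeats this analysis in subgroups.

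SAP 8.1, like protocol 9.5, says of the planned size: "With 150 evaluable subjects per trial group, there will be an 80% power to detect a difference between C21 and placebo". The assumed Day 60 mortality is 10% on placebo and 2.5% on C21. For the detection limit with 15 placebo deaths it states: "significance will be seen if at most 6 subjects die in the C21 group".

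The plan has no rule for a p-value and interval that disagree, or for an arm without deaths. The nearest text, in SAP 12.0, allows a factor to be dropped from a model if it causes convergence problems.

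**The concern.** The log-rank test is a score test. It is evaluated at a hazard ratio of 1, whereas the Wald interval uses a standard error evaluated at the estimate and assumes symmetry on the log scale. With many deaths the two agree. With about 19, perhaps 4 of them on C21, they can differ enough to fall on opposite sides of 1. A second source of mismatch is that the test is stratified by severity and region while the Cox model adjusts for them as covariates, so the two rest on different models.

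At stake is the presentation of the main result: a mortality p-value below 0.05 beside an interval that includes 1, or no usable interval. Both would have to be explained after unblinding.

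**Working it through.** **Inputs from the documents.** 150 per arm, 1:1; 10% versus 2.5% mortality; 5% withdrawal; two-sided 5% level (SAP 8.1, 8.2). Expected deaths: 150 × 0.10 + 150 × 0.025 = 15 + 3.75 = 18.75.

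**The plan's own figures.**
- Hazard ratio: ln(0.975)/ln(0.90) = 0.240, as stated.
- Power: 78.4% by simulated log-rank test with 5% withdrawal and 79.8% by a variance-corrected formula, both close to the stated 80%.
- Detection limit: 15 versus 6 deaths gives log-rank p of about 0.042, and 15 versus 7 gives about 0.076. The stated limit reproduces.

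**Wald interval at 15 versus 6.** The standard error of the log hazard ratio is about √(1/6 + 1/15) = 0.483.
- From death counts alone: hazard ratio 6/15 = 0.40, interval exp(ln 0.40 ± 1.96 × 0.483) = 0.155 to 1.031. The matching log-rank z is (15 − 6)/√21 = 1.964, p = 0.0495.
- Allowing for the shrinking risk sets: hazard ratio ln(0.96)/ln(0.90) = 0.387, upper limit exp(ln 0.387 + 1.96 × 0.483), which is just under 1.00.

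The limit therefore sits on 1, and the order of deaths and withdrawals decides the side. In simulated orderings it ranged from 0.957 to 1.040.

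**How often the test is significant and the Wald interval includes 1, at 15 versus 6.**
- Unadjusted: 52% of orderings without withdrawals, 45% with 5% withdrawal.
- Stratified test with covariate-adjusted Cox model: 21% to 27% in three simulations, and 15% in a variant with strata unbalanced between arms.

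Values not in the documents: the adjusted runs took score 6 to carry three times the risk of score 5; the main run also took 25% of subjects with score 6, an even region split and uniform death times.

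**Other splits.** With the adjusted analysis, disagreement was absent at 15 versus 5 and 16 versus 6, and at most 0.5% at 14 versus 5. It was 41% at 12 versus 4, 88% at 10 versus 3, 38% at 9 versus 2 and 100% at 7 versus 1. Fewer deaths overall make it more common.

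**Under the design assumptions.** About 3.5% to 4.0% of all trials show the disagreement, or about 4.5% of the significant ones.

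**No C21 deaths.** Probability 0.975^150 = 2.2% (3.0% simulated with withdrawals). The log hazard ratio then diverges and no Wald interval exists. Dropping a factor cannot help, because treatment is the factor at fault. In subgroups the case is more likely: 0.975^75 = 15% with 75 C21 subjects, and 0.975^15 = 68% with 15, the size of a category at the 10% display threshold.

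**Alternatives.**
- Score interval: median upper limit 0.97 at 15 versus 6. With 15 versus 0 and equal risk sets, the limit solves √(15 × HR) = 1.96, so HR = 3.84/15 = 0.26, which is finite.
- Profile likelihood: median 0.14 to 0.95 at 15 versus 6, below 1 in every unadjusted ordering (about 1% of misses with unbalanced strata). With 15 versus 0 the upper limit is about 0.13. It can err the other way. At 8 versus 2, log-rank z = 6/√10 = 1.897 (p = 0.058), but the likelihood-ratio statistic 2[8 ln(8/5) + 2 ln(2/5)] = 3.855 exceeds 3.841, so the interval excludes 1. In unadjusted simulation this happened in 100% of orderings at 8 versus 2, 64% to 68% at 13 versus 5, and about 1.6% of trials under the design assumptions.

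**The case against.** The strongest reply is that nothing is decided by this interval. SAP 12.5.1 applies the 5% level to the log-rank p-value, SAP 12.0 gates the hierarchy on test significance, and the Cox model only describes the size of the effect. That stands in full. A reader might infer that the primary conclusion, its error rate or its power is compromised; the documents do not support this, because they already say which statistic governs.

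The second reply is that 15 versus 6 is a knife edge. Under the design assumptions that exact split has about a 1% chance (0.108 × 0.09). This too stands, and it is why the figure to carry forward is about 4% of trials. It does not dispose of the point, since the disagreement becomes common if mortality falls below the assumed 10%. Protocol 2.2 reports 3 deaths among 56 placebo subjects in phase 2, about 5%, though in a different population with shorter follow-up.

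The third reply is that a log-rank p-value beside a Cox Wald interval is a clear, pre-specified choice. That is fair: the text is neither ambiguous nor contradictory. A reader might also infer that profile likelihood removes the conflict altogether. It does not, because it inverts the likelihood-ratio test rather than the log-rank test, and its remaining disagreements include a non-significant primary test beside an interval that suggests benefit.

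**Conclusion.** The point holds as a reporting weakness of minor weight. At the stated detection limit the test and the Wald interval conflict in roughly 20% to 50% of orderings. Under 10% versus 2.5% mortality with 150 per arm, they conflict in about 4% of all trials, and in about 2% more there is no Wald interval. The unadjusted figures and the zero-death probability follow from the plan's own inputs and the assumed timing of deaths and withdrawals. The lower end of the 20% to 50% range also depends on the assumed severity and region structure. Decision, type I error and power are unaffected.

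**What to change.** In SAP 12.5.2.2, and for the subgroup repeats in 12.5.2.4:
- Fit the Cox model stratified by severity and pooled region, so that it matches the test. In subgroups, omit any factor that defines the subgroup, as SAP 12.0 already provides.
- Replace the Wald interval with a 95% interval that inverts the stratified log-rank (score) test, using the same handling of tied death days. It agrees with the p-value by construction and has a finite upper limit when no C21 subject dies.
- If one arm has no deaths, report the one-sided bound and the death counts.

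A profile-likelihood interval is an acceptable simpler alternative. It removes almost all cases of a significant test beside an interval that includes 1, at the price of the reverse conflict in about 1.6% of trials under the design assumptions.

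The cost is a short SAP edit before unblinding and slightly more programming. Protocol section 3 and protocol 9.3.2 promise only a hazard ratio with a 95% interval and do not name its type, so no protocol amendment is needed.

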12.5.2.3 Sensitivity Analyses

1. Subjects with any important protocol deviations (as defined in Section 12.4) that impact efficacy, who prematurely discontinue IMP will be excluded from the analysis. In the primary analysis, subjects with important protocol deviations could falsely draw the estimated treatment difference closer. Exclusion of these subjects in this sensitivity analysis will help assess the magnitude, if any, of this effect. Additionally, subjects withdrawn from treatment due to patient decision may be excluded. For subjects in the PP, the analysis approach as described in Section 12.5.2.2 for primary analysis will be followed.
2. The proportion of deaths before or at Day 60 between treatment groups will be compared using a logistic regression model adjusting for randomized treatment, actual baseline disease severity and region as per Appendix 2 on the ITT. Subjects with no confirmed death or missing data due to premature withdrawal will have missing data imputed as per Section 10.19.2. The number of deaths at Day 60, the adjusted proportions as calculated from Ge et al., 2011, and the associated statistics (treatment difference (C21-Placebo), SE and CI) will also be presented.
3. Sensitivity to IMP discontinuation: No analysis will be performed to assess the impact of IMP discontinuation. Subjects who prematurely discontinue due to subject decision up to Day 11 will be excluded from the PP set since this is equivalent to less than 80% compliance.

12.5.2.4 Supplementary Analyses

Additional analyses examining the consistency of the intervention effect in the following subgroups using the ITT will be performed. A forest plot and repeat of the analysis as per Section 12.5.2 in the following subgroups will be presented:

- Age group: <65 vs ≥65 years
- Sex: female vs male
- Actual baseline disease severity (8-point ordinal scale 5 or 6 at Day 1)
- Race (American Indian or Alaska Native, Asian, Black or African American, Native Hawaiian or Other Pacific Islander, White or Other)
- Ethnicity (Hispanic or Latino, Not Hispanic or Latino)
- Region (Europe, Rest of the World)
- Presence of risk factors for severe COVID-19 (Yes, No)

The subgroup categories may be redefined prior to unblinding the study due to the following reasons:

- If the number of subjects is too small (less than 10% of the ITT population) within a subgroup then only the categories with >10% of subjects will be presented in the output.
- If other subgroups appear to be of interest (for example the medications used as SOC) they will be included in the summary.

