9.3.6. Other Analyses

The subject flow including total number of screened subjects, number of randomized subjects, completers, withdrawn subjects (including reason for withdrawal) and subjects included in each of the analysis sets will be summarized by treatment group and for the total.

The number of subjects with major protocol deviations will be summarized by category of violation and by treatment group including subset of major protocol deviations leading to exclusion from the per-protocol analysis set.

Demographic and baseline characteristics will be summarized using descriptive statistics for each treatment group and for the total number of randomized subjects. Medical history will be coded using MedDRA and summarized by system organ class and preferred term for each treatment group. Prior medications will denote medications used prior to first dose of IMP independent of if stopped at randomization or not. Concomitant therapy will denote medications started prior to but continuing after randomization or medications with a start date at or after the randomization date. Prior and concomitant therapy will be summarized separately by Anatomical Therapeutic Chemical levels 2 and 4.

Several sensitivity analyses will be performed on the primary and key secondary endpoints regarding choice of population (PP population) and choice of imputation for missing data. Specifically tipping point analyses will be performed on key secondary endpoints based on the ordinal scale.

Subgroup analyses of the primary and key secondary endpoints will be made to assess consistency of the intervention effect across at least the following subgroups:

- Age group: <65 vs ≥65 years
- Sex: female vs male
- Baseline disease severity (8-point ordinal scale 5 or 6 at Day 1)

- Race (American Indian or Alaska Native, Asian, Black or African American, Native Hawaiian or Other Pacific Islander, White or Other)
- Ethnicity (Hispanic or Latino, Not Hispanic or Latino)
- Region (North America, South and Central America, Europe, Africa, or Asia)
- Presence of risk factors for severe COVID-19 (Yes, No)

If the number of subjects is too small (less than 10%) within a subgroup, then the subgroup categories may be redefined prior to unblinding the trial. Further details on the statistical analysis will be provided in the SAP.

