12.0 Statistical Methods

All statistical analyses will use SAS® version 9.4 or higher. Unless otherwise noted, categorical variables will be summarized using counts and percentages. Percentages will be rounded to one decimal place, except 100% which will be displayed without any decimal places and percentages will not be displayed for zero counts.

Continuous variables will be summarized using the number of observations (n), mean, Standard Deviation (SD), median, Q1, Q3, minimum and maximum. The minimum and maximum values will be displayed to the same level of precision as the raw data, the mean, median, Q1, and Q3 to a further decimal place and the SD to two additional decimal places. The maximum number of decimal places will be 4, unless otherwise noted. P-values will be presented to 3 decimal places, with values less than 0.001 presented as <0.001.

In general, all data summaries will be presented by treatment group and overall. Efficacy outputs will not have an overall column. If not stated otherwise, p-values from statistical tests will be two-sided and CIs will be calculated using a 95% CI.

Stratification will be done based on baseline disease severity, that is the score on the ordinal scale at baseline (5 or 6), and region (North America, South and Central America, Europe, Asia, Africa). The actual stratification will be used as factors in the statistical analysis, subjects included in wrong stratum at randomization will be moved to their correct strata belonging in the analyses. Small stratum may be pooled in the analysis. Any pooling of stratum will be agreed prior to unblinding of the database. Region will be pooled as Europe vs the rest of the world (North America, South and Central America, Asia, Africa). For all models where region is a factor (including in the imputation), pooled region will be used. In the text of this document, region will mean pooled region. Factors may be removed from models if the factor is causing an issue with convergence. For subgroup analysis, factors that are aligned with the strata division will be deleted from the model.

Missing data will be handled as described in Section 10.19. The ITT is used to analyze endpoints related to the efficacy objectives, the PP will be used for sensitivity analyses related to efficacy objectives and the SS is used to analyze the endpoints and assessments related to safety. PK analyses will be presented using the PKS.

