12.5.3.7 Supplementary Analyses

Additional analyses examining the consistency of the intervention effect for the key secondary endpoints will be performed for the subgroups as per Section 12.5.2.4 using the ITT.

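### The subgroup analyses aim to examine consistency of effect but plan no treatment-by-subgroup contrast; a separate rule leaves small categories out of the display

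*SAP*

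**What the plan says.** Protocol 9.3.6 plans subgroup analyses of the primary and key secondary endpoints that "will be made to assess consistency of the intervention effect". It names seven factors: age, sex, baseline severity, race, ethnicity, region and risk factors for severe COVID-19. SAP 12.5.2.4 adopts the same aim: "Additional analyses examining the consistency of the intervention effect in the following subgroups using the ITT will be performed". The means it gives are: "A forest plot and repeat of the analysis as per Section 12.5.2 in the following subgroups will be presented".

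The analysis to be repeated is in SAP 12.5.2.2. It is a stratified log-rank test with its p-value, and a Cox model with treatment, baseline severity and region as main effects, giving a hazard ratio with 95% CI. For the key secondary endpoints, SAP 12.5.3.7 says the analyses "will be performed for the subgroups as per Section 12.5.2.4 using the ITT". The only modelling rule for subgroups is in SAP 12.0: "For subgroup analysis, factors that are aligned with the strata division will be deleted from the model". Neither document contains a treatment-by-subgroup term, a heterogeneity test, or a criterion for calling an effect consistent or inconsistent.

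On small categories, Protocol 9.3.6 says that where a category holds under 10% of subjects, "then the subgroup categories may be redefined prior to unblinding the trial". SAP 12.5.2.4 opens with the same allowance, but the rule it then gives is "then only the categories with >10% of subjects will be presented in the output".

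**The concern.** Consistency is a statement about the difference between subgroup effects. The planned output gives each subgroup effect separately and leaves the comparison to the reader's eye. Because p-values are part of what is repeated, the natural shortcut is to note that one category is significant and another is not. In a trial sized for the overall effect, that pattern is common even when the effect is the same everywhere. It could be read as benefit confined to one group.

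The volume of output adds to this: 7 factors x 5 endpoints = 35 comparisons, and so at least 70 within-subgroup analyses before small categories are dropped.

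The display rule is a second, separate matter. Subjects in a race category under 10% do not appear in the race panel. A two-level factor with one small level is reduced to a single row.

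**Working it through.** **Inputs.** SAP 8.1 and Protocol 9.5 give 150 per arm, Day 60 mortality of 10% v 2.5%, HR 0.24, 5% withdrawal, two-sided 5% and 80% power. Subgroup shares are not in the documents, so a range is shown. No power is stated for the key secondary endpoints.

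**The plan's own figures.**
- HR = ln(0.975)/ln(0.90) = 0.240, as stated.
- Power: simulated log-rank (exponential deaths over 60 days, 5% withdrawal spread uniformly) gives 0.778 to 0.795 over five runs. The arcsine two-proportion formula gives 0.806. Both agree with 80% to about 2 points.
- Detection limit: 15 v 6 deaths gives p = 0.042 (chi-square) or 0.0495 (approximate log-rank). 15 v 7 gives 0.076 or 0.088. The limit of 6 reproduces.

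**Chance that exactly one of two subgroups is significant under a constant effect.** The overall expected z is 1.96 + 0.842 = 2.80. A subgroup with share f has expected z = 2.80 x sqrt(f), and power = Phi(2.80 x sqrt(f) - 1.96). P(exactly one) = p1(1 - p2) + p2(1 - p1).

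| Split | Power in each subgroup | Exactly one significant |
|---|---|---|
| 50:50 | 0.51 / 0.51 | 0.50 |
| 30:70 | 0.34 / 0.65 | 0.55 |
| 20:80 | 0.24 / 0.71 | 0.61 |

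Simulation of the mortality endpoint with HR 0.24 in every subgroup gives 49%, 56% and 62-63%. Among trials where the overall test is significant, which is when subgroup claims tend to be made, the figures are 57%, 66% and 75%. An actual reversal of direction is much rarer: 5% at 50:50.

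**What a contrast would do in the same trials.** A difference in log hazard ratios tested at 5% flags heterogeneity in about 1.5% of the simulated trials (nominal rate 5%).

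**Limits of the contrast for mortality.**
- Expected deaths are 150 x 0.10 + 150 x 0.025 = 15 + 3.75 = 18.75.
- At a 50:50 split each subgroup has 7.5 placebo and 1.875 C21 deaths. The SE of the log ratio of HRs is sqrt(2 x (1/7.5 + 1/1.875)) = 1.15.
- Power is 9% for a 2-fold ratio of HRs and 16% for a 3-fold ratio. Reaching 80% needs a ratio of about exp(2.80 x 1.155) = 25.
- At least one arm of a subgroup has no deaths in 30% of simulated trials at 50:50, rising to 77% at 10:90. The Cox HR in that subgroup is then not finite.
- If independent, 35 contrasts each tested at 5% would give at least one false signal with probability 1 - 0.95^35 = 83%.

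**The case against.** The strongest reply is that the SAP does not judge consistency by subgroup p-values. A reader might infer that it does, because p-values are part of the repeated analysis, but no such rule is written. A forest plot of hazard ratios with CIs shows effect sizes and overlap. That stands: the 50 to 61% describes what happens if p-values are compared, not a planned decision.

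A reader might also infer that leaving out small categories makes a constant effect look inconsistent. The figures point the other way. At a 10:90 split, discordance is 71-72% and reversal 14%, so small categories are the most erratic and omitting them lowers apparent inconsistency. The fault there is one of display.

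Nor does the SAP clearly abandon the protocol's option to redefine categories. The 10% rule sits under a sentence that keeps that option, although omission is not redefinition. Region is already merged to Europe v the rest of the world. Omitted subjects remain in the overall ITT analysis.

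Finally, an interaction term is no cure for mortality. Its power is very low, a null result could be misread as proof of consistency, and a log-odds interaction would not match the planned risk differences. Merging the small level of a two-level factor simply restores the whole ITT set. These points limit what the fix can claim, but none of them supplies the missing contrast.

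**Conclusion.** The point holds in a limited form. The plan sets a question about consistency and does not produce the estimate that answers it. If subgroup p-values are compared, a constant effect looks discordant in about half to three fifths of trials per two-level factor, for splits from 50:50 to 80:20. This assumes the stated 80% power, non-overlapping subgroups and the shares shown. For key secondary endpoints, 80% is an assumption. At 90% overall power a 50:50 split is still discordant in 47%.

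The documents do not support saying that the SAP decides consistency by p-values, or that the 10% rule creates inconsistency. These analyses are labelled supplementary and lie outside the testing hierarchy. The change is an inexpensive improvement in reporting and does not bear on the primary result or the control of alpha.

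**What to change.** In SAP 12.5.2.4 and 12.5.3.7:

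1. For each factor and endpoint, add beside the forest plot the between-subgroup contrast with 95% CI, on the scale of the planned effect: ratio of HRs for mortality and sustained discharge, and difference in risk differences for the two Day 15 proportions. For oxygen-free days, use the difference in mean differences from the ANOVA already planned in 12.5.3.6. Label the contrasts descriptive and not adjusted for multiplicity.
2. State that within-subgroup p-values will not be used to judge consistency, and that a null contrast does not prove it.
3. Where an arm of a subgroup has no deaths, show event counts instead of an HR.
4. For factors with more than two levels, such as race, merge categories under 10% into Other. For a two-level factor with a level under 10%, show counts and make no comparison.

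The cost is some model terms and a few table columns, with no change to design, data collection or alpha. The drawbacks are wide intervals, above all for mortality with about 19 expected deaths, and possible attenuation for the imputed endpoints. The imputation model in SAP 10.19.1 has no treatment-by-subgroup terms and does not include sex, race, ethnicity or risk factors.
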